#### **7.1.5 Serious Adverse Events**

##### **7.1.5.1 Definition of a Serious Adverse Event**

A serious adverse event is an adverse event occurring at any dose that results in any of the following outcomes or actions:

- death
- a life-threatening adverse event (ie, the patient was at immediate risk of death from the event as it occurred); does not include an event that, had it occurred in a more severe form, might have caused death
- inpatient hospitalization or prolongation of existing hospitalization
- a persistent or significant disability/incapacity (refers to a substantial disruption of one’s

ability to conduct normal life functions)

- a congenital anomaly/birth defect
- an important medical event that may not result in death, be life-threatening, or require hospitalization, but may jeopardize the patient and may require medical intervention to prevent 1 of the outcomes listed in this definition

NOTE: Any suspected transmission of an infectious agent via a medicinal product is considered an important medical event.

Hospitalizations scheduled for an elective procedure or for treatment of a pre-existing condition that has not worsened during participation in the study will not be considered serious adverse events.

An adverse event that does not meet any of the criteria for seriousness listed above will be regarded as a nonserious adverse event.

#### **7.1.5.2 Reporting a Serious Adverse Event**

All serious adverse events (as described in section 7.1.5.1) that occur either during the study period (including the protocol-defined follow-up period), regardless of judged relationship to the study drug, or after the study period, if considered related to study drug or to the patient's participation in the study, must be immediately reported to ORION Pharmacovigilance . The report must be made within 24 hours of the investigator's knowledge of the event. In addition, a blood sample will be obtained for measurement of the concentration of IPP-201101 from all patients who have a serious adverse event recorded as related to study drug (see also section 7.1.6).

Within 24 hours of the investigator's awareness of the serious adverse event, the investigator must provide ORION Pharmacovigilance, by facsimile, with a signed Serious Adverse Event Transmittal Form completed to the greatest extent possible and a copy of all relevant source documents, including the corresponding completed adverse event, medical history, and concomitant medications pages of the CRF as appropriate. (For adverse event reporting instructions see section 7.1.2.).

If it is not possible to complete all sections of the SAE form within 24 hours, transmission of the form must not be delayed and the outstanding information should be sent on a follow-up SAE form.

If the SAE is reported by telephone, all points on the SAE form should be covered in the initial telephone report and followed by a completed and signed SAE form to confirm the verbal information previously reported.

Information on SAEs will be recorded on a specific Non Carbon Repeat (NCR) SAE form. Blank copies are included in the study Investigator's File.

The SAE form must be completed as fully as possible with information relevant to the SAE(s) being reported. All fields should be populated or marked accordingly if no information is available.

In cases of death reported as an SAE, the report should detail the main and contributory causes of death. This information should also be accompanied by a death certificate or autopsy report, if

available.

For all SAEs where important or relevant information is missing, active follow-up should be undertaken. Investigators or other site personnel should inform the ORION Clinical Services' Pharmacovigilance Department of any follow-up information on a previously reported SAE. The follow-up information must be presented on an SAE form marked as follow-up. It is necessary only to provide the new information, with the SAE form signed by an Investigator.

Investigators or other site personnel should send relevant or requested supporting documentation (e.g., ECG, laboratory results, autopsy report) to the Pharmacovigilance Department of ORION Clinical Services.

The Investigator will ensure that all the necessary information is provided within the timelines stipulated by the ORION Clinical Services' Pharmacovigilance Department when the request for information is made.

Follow-up reports should be completed and faxed following the same procedure as for the initial report.

In the US and European Union (EU), the facsimile to the sponsor is to be addressed as follows:

**Study Contact for Reporting Serious Adverse Events.**

ORION Clinical Services Ltd

[[contact]](mailto:[contact])

EU SAE [contact]

Back-up EU SAE [contact]

US SAE [contact]

Back-up US SAE [contact]

In the US, the investigator must ensure that the IRB is also informed of the event in accordance with local regulations.

In the EU, ImmuPharma or its designee must ensure that the IEC is also informed of the event in accordance with local regulations.

Each report of a serious adverse event will be reviewed and evaluated to assess the nature of the event and the relationship of the event to the study drug, study procedures, and to underlying disease. This will be done by the investigator and ImmuPharma or its designee. On the basis of this assessment, a decision will be made concerning the need for further medical intervention. If a serious, unexpected adverse event is believed to be related to the study drug or study procedures, ImmuPharma or its designee will take appropriate steps to notify all investigators participating in clinical studies of IPP-201101 conducted under ImmuPharma IND applications and the appropriate regulatory authorities.

In addition to notifying the investigators and regulatory authorities, other measures may be required, including the following:

- alteration of existing research by modification of the protocol

- discontinuation or suspension of the study
- alteration of the process of informed consent by modification of the existing consent form and informing current study participants of new findings
- modification of listings of expected toxicities to include adverse events newly identified as related to IPP-201101

#### **7.1.6 Withdrawal Due to an Adverse Event**

Any patient who experiences an adverse event may be withdrawn from the study at any time at the discretion of the investigator. If a patient is withdrawn wholly or in part because of an adverse event, both the adverse events page and termination page of the CRF will be completed at that time. In addition, a blood sample will be obtained for measurement of the concentration of IPP-201101 from all patients who have an adverse event assessed as related to study drug leading to withdrawal from the study (see also section 7.1.5.2). The patient will be monitored until the event has resolved or stabilized, until a determination of a cause unrelated to the study drug or study procedure is made, or until the patient is referred to the care of a local health care professional. The investigator must inform the medical monitor as soon as possible of all patients who are being considered for withdrawal due to adverse events. Additional reports must be provided when requested.

If a patient is withdrawn from the study for multiple reasons that include adverse events, the termination page of the CRF should indicate that the withdrawal was related to an adverse event.

Stopping rules and discontinuation criteria for any toxicity are described in section 3.6.

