### 3.6 Stopping Rules and Discontinuation Criteria

A patient may discontinue participation in the study at any time for any reason (eg, lack of efficacy, consent withdrawn, or adverse event). The investigator and/or sponsor can withdraw a patient from the study at any time for any reason (eg, protocol violation or deviation as defined in section 11.1.2, noncompliance, or adverse event).

An independent, external DSMB will oversee the safety of the patients enrolled in the study and monitor the occurrence of flare throughout the study. The DSMB will meet as specified in its charter. The DSMB may recommend stopping the study for safety concerns. Toxicity will be monitored using the Modified World Health Organization (WHO) Toxicity Criteria, which includes graded adverse events on a scale from 0 to 4 (see Appendix A). Individual patients will be withdrawn from the study if any of the following occur:

Event	Rule for withdrawing patient
Grade 2 event	The patient will be treated according to the investigator’s usual standard of care (SOC). If the event does not improve to grade 1 or less within 4 weeks from the onset of grade 2 severity, the medical monitor should be contacted to determine if the patient should be withdrawn from the study.

Grade 3 event (one grade 3 event not related to treatment)	The patient will be treated according to the investigator’s usual SOC. If the event does not improve to grade 1 or less within 4 weeks from the onset of grade 3 severity, the medical monitor should be contacted to determine if the patient should be withdrawn from the study.
Grade 3 event (one grade 3 event related to treatment or two grade 3 events not related to treatment)	The patient will be withdrawn from the study.
Grade 4 event (any grade 4 event, related or not related to treatment)	The patient will be withdrawn from the study.
Pregnancy	The patient will be withdrawn from the study.
Serious intercurrent illness or significant worsening of intercurrent illness (eg, diagnosis of any cancer, lymphoma or leukemia, anaphylaxis, severe infections)	The patient will be withdrawn from the study.
Severe flare	The patient will be withdrawn from the study.

This study may be prematurely terminated if, in the opinion of the DSMB or the sponsor, there is sufficient and reasonable cause. Written notification documenting the reason for study termination will be provided by the terminating party to all involved.

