### **5.2 Prior and Concomitant Therapy or Medication**

Any prior or concomitant therapy or medication given to a patient from the start of screening or during study drug administration will be indicated on the CRF. Other medications used for SLE or other disorders will also be captured on the CRF, as detailed below. Dosage and generic name or trade name will be indicated. The sponsor will encode all therapy and medication according to the WHO drug dictionary (WHO Drug).

As described in section 4.1, if the patient is using oral corticosteroids, the weekly cumulative dose must not exceed 80 mg of prednisone equivalent; the weekly dose must be stable over the 4 weeks preceding the 1st dose of study drug. If a patient is taking oral corticosteroids at study entry, the dose may be decreased during the study at the investigator's discretion. The dose of background corticosteroid medication may be increased to treat the patient for minor fluctuations in lupus disease activity (ie, a mild or moderate flare). However, the dose of oral corticosteroid may not exceed 30 mg of prednisone or equivalent per day for more than 2 weeks. If a patient not previously treated with corticosteroids requires initiation of treatment with corticosteroids during the study to treat minor fluctuations in lupus disease activity (ie, a mild or moderate flare), the dose of oral corticosteroid may not exceed 30 mg of prednisone or equivalent per day for more than 2 weeks. If a patient requires a temporary increase in corticosteroid dose or a short course of corticosteroid treatment (ie, 2 weeks) and the medication is unable to be tapered to the baseline dose or be withdrawn, respectively, the patient is to be withdrawn from the study. If a patient requires treatment with corticosteroids for a condition other than SLE, these same restrictions on corticosteroid use, and those detailed in section 4.2, will apply. The use of intra-articular steroids may be allowed after consultation with the medical expert.

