### **7.1 Adverse Events**

#### **7.1.1 Definition of an Adverse Event**

An adverse event is any untoward medical occurrence in a patient that develops or worsens in severity during the conduct of a clinical study of a pharmaceutical product and does not necessarily have a causal relationship to the study drug. An adverse event can, therefore, be any unfavorable and unintended physical sign, symptom, or laboratory parameter that develops or worsens in severity during the course of the study, or significant worsening of the disease under study (or any concurrent disease), whether or not considered related to the study drug.

Accordingly, an adverse event could include any of the following:

- intercurrent illnesses
- physical injuries
- events possibly related to concomitant medication
- significant worsening (change in nature, severity, or frequency) of the disease under study or other pre-existing conditions. (NOTE: A condition, recorded as pre-existing, that is intermittently symptomatic [eg, headache] and which occurs during the study should be

recorded as an adverse event.)

- drug interactions
- events occurring during diagnostic procedures or any washout phase of the study
- laboratory or diagnostic test abnormalities occurring after the start of the study (ie, after screening and once confirmed by repeat testing) that results in the withdrawal of the patient from the study, requires medical treatment or further diagnostic work-up, or is considered by the study investigator to be clinically significant.

NOTE: Abnormal laboratory test results at the screening visit that preclude a patient from entering the study or receiving study treatment are not considered adverse events, but will be recorded to monitor data from patients who do not meet screening criteria.

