### **10.7.3 Safety Analysis**

For continuous variables, descriptive statistics (n, mean, SD, median, minimum, and maximum) will be provided for actual values and changes from baseline to each time point, including endpoint. For categorical variables, patient counts and percentages will be provided. Descriptive summaries of serious adverse events, patient withdrawals because of adverse events, and clinically significant abnormal values (clinical laboratory or vital signs values) on the basis of predefined criteria will also be provided. Summaries will be presented by treatment group and for all patients.

All adverse events will be coded using the Medical Dictionary for Regulatory Activities (MedDRA). A patient will be counted only once in each preferred term or system organ class category for the analyses of safety. Summaries will be presented for all adverse events (overall and by severity), adverse events determined by the investigator to be treatment related (overall and by severity), serious adverse events, and adverse events causing withdrawal from the study. Summaries will be presented by treatment group and for all patients. Patient listings of deaths, other serious adverse events, and adverse events leading to withdrawal will be presented.

Changes in laboratory and vital signs measurement data will be summarized descriptively. All values will be compared to prespecified boundaries in order to identify clinically significant changes or values, and such values will be listed.

Newly occurring physical examination abnormalities will be identified and listed.

The use of concomitant medications will be summarized by therapeutic class using descriptive statistics. Concomitant medications will include all medications taken while the patient is treated with study drug. Concomitant medication usage will be summarized as present at screening, ongoing at baseline/start of study drug treatment (visit 2 [week 0]), and started any time after visit 2 (week 0) through visit 16 (week 52).

Cumulative positive C-SSRS outcomes during the study will be summarized by treatment group.

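### Severe-flare withdrawals can be recorded as adverse-event withdrawals, which mixes efficacy failure with toxicity in the by-arm total and can move those patients into multiple imputation in the first sensitivity analysis

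*Protocol*

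**What the plan says.** Section 7.1.1 includes in the definition of an adverse event "significant worsening of the disease under study (or any concurrent disease), whether or not considered related to the study drug". Its list of examples repeats the point: "significant worsening (change in nature, severity, or frequency) of the disease under study or other pre-existing conditions".

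Section 7.1.6 deals with withdrawals that have several reasons. If an adverse event is among them, "the termination page of the CRF should indicate that the withdrawal was related to an adverse event".

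Section 3.6 has a table of withdrawal rules for individual patients. One row requires withdrawal for "one grade 3 event related to treatment or two grade 3 events not related to treatment", and another for any grade 4 event whatever its cause. Severe flare is a separate row. It is also listed there as a treatment failure, and 7.1.7 gives it a section of its own. No row says whether a lupus manifestation belongs under the toxicity grades or under flare.

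Section 5.2 allows mild or moderate flares to be treated on study: "The dose of background corticosteroid medication may be increased to treat the patient for minor fluctuations in lupus disease activity".

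Section 10.7.3 plans summaries by treatment group that include "serious adverse events, and adverse events causing withdrawal from the study". It describes no separate line for lupus activity.

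Section 10.6.3.1 makes every withdrawal a nonresponder in the primary analysis. In the first sensitivity analysis, only withdrawals for lack of efficacy are failures. The rest are multiply imputed within treatment group and randomization stratum.

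**The concern.** A severe SFI flare will ordinarily also be a significant worsening of lupus, and so an adverse event under 7.1.1. The 7.1.6 rule then lets the adverse-event label take precedence on the termination page. Two analyses depend on that label.

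The first is the total of adverse-event withdrawals by arm. If the drug works, flare withdrawals should be commoner on placebo, while true drug toxicity would be commoner on active. Added together, the two offset each other. If the drug made lupus worse, the total would rise on active without showing why.

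The second is the first sensitivity analysis. A patient withdrawn for severe flare is an efficacy failure in any ordinary sense. Labelled as an adverse-event withdrawal, that patient is no longer set to failure and can be imputed as a responder.

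**Working it through.** **What the protocol gives.** It states no flare-withdrawal or toxicity-withdrawal rate for this trial, so there is no figure of its own to reproduce on this point. Its one design figure is power with 100 patients per arm and a placebo response of 40% to 45%: at least 90% for a 25-point difference and 80% for 20 points. These reproduce (94.9% to 95.3%, and 81.2% to 81.6%). They matter here only because they show that the design expects disease activity to differ between arms.

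**Effect on the total.** Let f be the proportion withdrawn for flare and recorded as an adverse event, and t the toxicity-withdrawal proportion among the others. The total is f + t(1 − f). All rates are assumptions, with t = 2% placebo and 7% active (a true excess of 5 points).

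| Flare withdrawals labelled AE, placebo / active | Placebo total | Active total | Difference |
|---|---|---|---|
| 15% / 8% | 0.15 + 0.02 × 0.85 = 16.7% | 0.08 + 0.07 × 0.92 = 14.4% | −2.3 points |
| 10% / 6% | 0.10 + 0.02 × 0.90 = 11.8% | 0.06 + 0.07 × 0.94 = 12.6% | +0.8 point |
| 7.5% / 4% (half of the first row labelled AE) | 0.075 + 0.02 × 0.925 = 9.35% | 0.04 + 0.07 × 0.96 = 10.72% | +1.4 points |

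If the two kinds of withdrawal are treated as disjoint, the difference in totals is the toxicity excess minus the placebo excess of lupus withdrawals. Take toxicity withdrawals of 10 active and 4 placebo per 100:

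- lupus 5 and 5: totals 15 and 9 (+6, excess intact);
- lupus 6 and 9: totals 16 and 13 (+3);
- lupus 6 and 12: totals 16 and 16 (0);
- lupus 5 and 15: totals 15 and 19 (−4).

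Full offset therefore needs a placebo excess of lupus withdrawals as large as the toxicity excess. With equal lupus rates the excess survives but stands out less. As a yardstick only, since safety is not tested, a two-sided 5% comparison has about 38% power for 10 v 4 and about 26% for 15 v 9.

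**Effect on the first sensitivity analysis.** Suppose all flare withdrawals are labelled AE and imputed at the planning response rates (placebo 40% to 45%, active 25 points higher at 65% to 70%). Expected responders per 100 patients, where failure coding would give none:

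- flares 15 placebo and 8 active: placebo 15 × 0.40 to 0.45 = 6.0 to 6.75; active 8 × 0.65 to 0.70 = 5.2 to 5.6; the treatment difference moves by −0.8 to −1.15 points;
- flares 10 and 6: placebo 4.0 to 4.5; active 3.9 to 4.2; it moves by −0.1 to −0.3 point;
- flares 10 and 10: placebo 4.0 to 4.5; active 6.5 to 7.0; it moves by +2.5 points.

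Both response rates rise, and the net effect can go either way.

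**3.6 against 5.2.** Appendix A grades disabling arthralgia as 3. Two flares that are mild or moderate by SFI but each reach that grade are treatable on study under 5.2, yet meet the 3.6 withdrawal row for two unrelated grade 3 events. The text does not say which governs.

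**The case against.** The case on the other side is substantial.

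- **Not every flare is caught.** A reader might infer that every severe-flare withdrawal enters the adverse-event summary. The text does not say so: flare has its own row and section, and 7.1.6 applies only when the reasons include an adverse event. This stands. What remains is that 7.1.1 and 7.1.6 permit the label and nothing prevents it.
- **The 3.6 rows do not compare arms.** A reader might think toxicity is cancelled within those rows. They are rules for individual patients and set no study stopping threshold, so any offset arises only in the by-arm totals. This stands.
- **Many lupus items grade low.** In Appendix A, pericarditis with rub, chest pain or ECG changes is grade 2, and a platelet count just under 100,000 is grade 1. Section 7.1.2 also collects related signs under one diagnosis. Two unrelated grade 3 lupus events will probably be uncommon. And 5.2 need not contradict 3.6, since permission to treat a flare does not promise continued participation. The passages need reconciling, but this is not a flat contradiction.
- **Other outputs show toxicity.** Preferred-term and organ-class tables, the treatment-related summary, patient listings, the separate flare endpoints and the specific event required by 4.3 leave much of an excess visible. This stands as partial mitigation. Relatedness is the investigator's judgement, and an excess spread over many terms is hard to see with about 100 patients per arm.
- **The size is unknown.** None of the seven serious adverse events listed for study IP-004 was a lupus flare.
- **Table splits are usually left to the SAP**, which is not at hand. That is fair for 10.7.3. The termination-page instruction, however, is fixed in the protocol.

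**Conclusion.** The point holds in limited form. The protocol lets a severe-flare withdrawal be recorded as an adverse-event withdrawal, so the by-arm total can mix efficacy failure with toxicity. That can dilute a toxicity excess and, under some assumed rates, offset or reverse it. The illustrations run from no loss of the excess to a change of sign, and all rest on invented rates and on how many flare withdrawals receive the label.

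A reader might go further and conclude that the trial could not detect toxicity, or that toxicity should be judged on non-lupus events alone. The documents support neither. The term-level tables and listings remain, and worsening of lupus caused by the drug would itself be a harm. Section 1.3.2.4 reports a trend below placebo with another formulation.

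The effect on the first sensitivity analysis follows from the same label. It is about 1 point or less on the treatment difference in two of the assumed cases and 2.5 points in the third. The primary analysis is untouched because all withdrawals are nonresponders. The correction is worth making because it is cheap and the label cannot easily be repaired after the data are collected.

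**What to change.** In 7.1.6, have the termination page record which 3.6 trigger led to withdrawal (toxicity, severe flare or other treatment failure) alongside the adverse-event entry. In 10.6.3.1, use that trigger to define lack-of-efficacy withdrawals for the first sensitivity analysis.

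In 10.7.3, or in the SAP, keep the all-event summaries. Also show adverse-event withdrawals, grade 3 to 4 events and serious events split into lupus activity and other, using the SFI and disease-activity forms already collected. Classify events blinded, before database lock. Do not rest the safety conclusion on the non-lupus part alone.

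The sponsor should reconcile 3.6, 5.2, 7.1.1 and 7.1.7 on which withdrawal row a lupus manifestation falls under. No clinical rule is proposed here.

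The cost is one extra field on the termination page, a split of tables already planned, and some judgement in classifying events.
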